## 8.12.4.3. Assessing the Psychological Impact of Study Participation

The psychological impact of study participation will be assessed by a mailed questionnaire prior to the 3 month clinical visit and by self-completed questionnaire at the 6, 15, 27 month study visits, and annually thereafter. If questionnaire data cannot be obtained due to missed study visits, or insufficient time to complete the questionnaire during a study visit, the information may be obtained by mail, telephone interview, or at the next study visit.

Should anyone drop out of the study or develop Type 1 Diabetes, the Parent Experiences Questionnaire will be given in clinic, mailed or completed online to assess participant experiences in the TEDDY study and reasons for dropout. These data will be obtained from the child's primary caretaker, usually the

mother. On an elective basis, fathers/partners will be invited to participate. They will be given the same questionnaires as given to the primary caretakers.

Once the child is 10 years of age, the psychological impact of study participation on the child will be added to the protocol as part of the annual assessment. Data collection from children below the age of 10 may be conducted on an elective basis.

Children who withdraw from the study or who develop Type 1 Diabetes will complete a Child Experiences Questionnaire if he/she is at least 10 years of age. The questionnaire will be given in clinic, mailed or completed online.

# 8.12.4.3.1. Parents' distress (anxiety and depression) in response to infant's at-risk status

The 20-item State portion of the State-Trait Anxiety Inventory (STAI) (Spielberger et al., 1970) is a reliable assessment instrument for assessing situation-specific anxiety in the U.S. and internationally. It has been used in several studies assessing anxiety in islet cell antibody positive (ICA+) children and adults and their family members (Johnson et al., 1990; Roth et al., 1994; Johnson and Tercyack, 1995; Roth et al., 1996; Johnson and Carmichael, 2000; [name] et al., submitted). It has also been used to assess anxiety in mothers after they were told their infant was genetically at-risk for type 1 diabetes in PANDA (Prospective Assessment in Newborns of Diabetes Autoimmunity) (Carmichaelet al., 2003; Johnson et al., 2004) and BABY DIAB ([name] et al., submitted). We propose to use a 6-item short form of this instrument in the self-completed questionnaire filled out prior to the initial 3-month clinic visit as well as at the 6-, 15-, and 27-month visits. In a sample of over 400 PANDA mothers, whose infants were genetically at-risk for diabetes, the six-item short form correlated highly with the STAI full scale (r = .95) and showed excellent internal consistency ( $\alpha = .92$ ).

In addition, at any time during the study, should a child show evidence of persistent autoimmunity (a positive autoantibody test result on two consecutive occasions), parental reactions to the news of the child's increased diabetes risk will be assessed using the 6 item short form STAI at the child's next clinic visit. Although there is a small literature assessing the initial impact of telling a mother that her child is at increased risk for TIDM, there are no longitudinal studies assessing the impact of learning a genetically at-risk child is showing evidence of further progression toward diabetes.

At the 6-month clinic visit, parental depression will be assessed by the Edinburgh Postnatal Depression Scale administered as part of the selfcompleted questionnaire. In a recent study of 192 PANDA mothers with

at-risk infants, Edinburgh Postnatal Depression Scale scores were reliable ( $\alpha = .89$ ) and predictive of the mother's understanding of risk (higher depression scores were associated with underestimating risk), anxiety (higher scores were associated with higher anxiety) and study drop out (higher scores were associated with early study drop-out) (Hood, 2003). A brief 6-item Depression Scale from Bradley's Well-Being Questionnaire will be included in the self-administered parent questionnaire completed at the 15 - and 27-month study visits. This scale has been previously used in World Health Organization (WHO) studies and has been translated into several languages.

After 27 months, we propose to collect measures of parental psychological stress/function annually. We will conduct an interim analysis of data collected from the primary caretaker through 27 months to guide us in terms of retaining the psychological stress/function measures or adding new ones.

At 39 months, we will add questions to the parental/primary caretaker's annual assessment that address the parent's or primary caretaker's perceptions of the child's function and well-being (e.g., does the caretaker overprotect, stigmatize or treat the child differently because the child is atrisk for diabetes). Under consideration are Parsons et al's (2002) rejection/protection index and adjective checklist approach used with four year old boys with Duchenne muscular dystrophy identified through newborn screening. However, since it will be more than three years before these assessments will be conducted, in two years we will conduct a through review of the available literature to identify the best available instrument for this purpose.

### 8.12.4.3.2. Child reactions to study participation and at-risk status

We expect families to differ considerably in terms of when they choose to inform a child of his or her increased risk status. Parents will be encouraged to make their own decision in this regard. However, appropriate expertise will be available at each site to assist parents in determining at what age the child should be informed and what language should be used to assure adequate understanding. TEDDY will develop written materials appropriate for various ages as well as suggested ageappropriate language to use when explaining the child's increased TIDM risk.

Children who are so informed and who are at least 10 years of age will be assessed for their reactions to their increased risk status, general psychological function, and reactions to study participation. Reactions to their increased risk status will be assessed using strategies previously employed with children in the DPT-1 and with children who are ICA+

(Johnson 1990, 1995, 2000, 2002). General functioning will be assessed by Harter's Self Perception Profile for Children or Adolescents. Assessments will be conducted annually. Given the demands on staff to conduct assessments of children less than 10 years of age, such assessments will be considered elective. Since assessments of the child will begin 5-10 years after the child enters TEDDY, we will consider alternative child assessment measures 5 years post-TEDDY inception. For example, should the National Children's Study be under way, we may want to select some measures used in that large-scale longitudinal study to assess functioning of TEDDY children.

# 8.12.4.3.3. Behavior changes the family may make in an effort to prevent the disease in the child

Data from several sources suggest that individuals who believe themselves to be at-risk for diabetes report behavior changes in an effort to prevent the disease. In Belgium, a large majority (73%) of adults with a first degree diabetic relative indicated that they would engage in life style changes if the results of a screening program indicated they were at high risk for the disease (Hendrieckx et al., 2002). Over half of the U.S. participants in the insulin injection arm of the Diabetes Prevention Trial -Type 1 Diabetes (DPT-1) indicated they made some sort of behavior change in an effort to prevent the disease; this was true for both the experimental (insulin injections) and control (watchful waiting) arms of the trial (Johnson et al., 2002). Among ICA+ children, half reported making behavior changes in an effort to prevent the disease; behavior change was associated with greater initial anxiety in response to the news of ICA+ status (Johnson and Tercyack, 1995). Over 60% of mothers of genetically at-risk infants, who were interviewed 2-4 years after learning of their infant's increased risk, indicated that they made behavior changes in an effort to prevent the disease in the child. The most common changes reported were: changes in diet (33%) and exercise (12%), efforts to reduce risk of illness of infection (9%), and increased monitoring of the child for signs and symptoms of diabetes (57%) (Baughcum et al., 2003). Across studies, dietary changes were the most often reported although increased monitoring by parents of at-risk children has been commonly reported as well.

In TEDDY, behavior changes initiated by parents in an effort to prevent diabetes in the child will be assessed by two questions as part of the self-completed questionnaire assessment at the 6-, 15-, 27-month study visits and annually thereafter. A TEDDY Participant Survey to be administered at the completion of TEDDY or at the time the parent leaves the study also assesses behavior changes made in an effort to prevent diabetes in the child.

#### 8.12.4.4. Family satisfaction with participation in the study protocol

Parental satisfaction with study participation will be assessed by 3 items on the self-completed questionnaire administered at 6, 15, 27 months and annually thereafter. At the end of the study, all parents will be given a detailed participant survey evaluating all components of the study. Dropouts will be given this survey, by telephone if necessary, at the time they leave the study. Child satisfaction with study participation will be assessed on an annual basis with youngsters 10 years or older who have been informed of their at-risk status. At the end of the study, all children will also be given a detailed participant survey evaluating all components of the study.

## 8.12.4.5. Psychosocial Stress as a Potential Trigger for Type 1 Diabetes

Stress has long been considered a potential trigger for TIDM (Danowski 1963). Psychological stress may affect the immune system in a variety of complex ways (Leclere 1989; Saravia-Fernandez et al., 1996). A number of retrospective studies have found stressful life events to be associated with disease onset (Slawson et al., 1963; Stein, 1971; Kisch, 1985; Robinson, 1985; Robinson et al., 1989; Vialettes, 1989; Dahlquist et al., 1991; Hagglof et al., 1991; Thernlund et al., 1995). However, not all investigators have found a link between stress and diabetes onset (Littorin et al., 2001). Further, most previous studies have used retrospective reports of stress, which are methodologically flawed.

In a prospective study of individuals screened for islet cell autoantibodies, Roth and her colleagues found a greater number of loss experiences during the year before the screening procedure in ICA+ families compared to ICAfamilies (Roth et al., 1994; Roth et al., 1996). In the DPT-1, negative life events were also assessed at the time of ICA screening, before the results were known. Negative life events were not predictive of ICA+ status in children or adults. However, negative life events were associated with increased illness which, in turn, was associated with ICA+ status (La Greca et al., 2000). Others have argued that psychological mechanisms serve as mediating variables between a number of disparate risk factors and the development of type 1 diabetes (Sepa et al., 2002).

### Procedures

In TEDDY, psychological stress will initially be prospectively measured in two ways: (1) negative life events documented in the study's baby book by the parent and updated at each study visit, and (2) paternal or primary caretaker anxiety and depression measured by self-completed questionnaire. Once the child reaches 10 years of age and is informed of his/her at-risk status, measures of stressful life events and child functioning will be obtained from the child.

#### Measures

#### 8.12.4.5.1. Number, nature and timing of negative life events

The number, nature, and timing of negative life events affecting the parent and the child will be assessed by a checklist in the TEDDY Book, filled out by the parent at home, and reviewed and updated at each study visit. Items on the checklist were selected from previously used life events checklists, including those used in the DPT-1 and in ongoing European studies with this population (DiPiS; BABYDIAB).

Once the child reaches 10 years of age and is informed of his/her at-risk status, the child will be invited to complete a standardized life events checklist developed specifically for children and adolescents.

### 8.12.4.5.2. Parental anxiety and depression

Parents or primary caretakers who are anxious and depressed create a stressful environment for the child. As stated previously, we plan to measure parental anxiety using the 6-item short form of the State Trait Anxiety Inventory. We also plan to measure post-partum depression at 6 months using the Edinburgh Postnatal Depression Scale and general depression at 15 and 27 months using the 6-item Depression scale of the Well-Being Questionnaire. After 27 months, parental or primary caretaker psychosocial functioning will be assessed on an annual basis. Our interim analysis of data collected from the parents or primary caretakers through 27 months will guide us in terms of retaining the 6-item State Trait Anxiety Inventory and the Depression scale of the Well-Being Questionnaire on the annual assessments or selecting alternative measures of parental/primary caretaker psychological stress and functioning.

### 8.12.4.5.3. Child psychosocial functioning

As discussed previously, once the child is 10 years of age and has been informed of his/her at-risk status, the child's reactions to his/her at-risk status, study participation, as well as general psychosocial functioning will be assessed on an annual basis. Assessment in youngsters younger than 10 years of age may be conducted on an elective basis. These measures may be used to assess whether highly stressed children progress to diabetes sooner than non-stressed children.

## 8.12.4.6. Internalizing Behavior and Psychosocial Stress as a Potential Trigger for Type 1 Diabetes

The Child Behavior Checklist (CBCL) is a well-validated instrument originally developed by [name] that has been used extensively worldwide for over 25 years. It is a measure of internalizing behavior (affective and anxiety problems) and externalizing behaviors (attention deficit/hyperactivity problems and oppositional defiant problems) and will be completed by one of the child's parents when the child is 3.5, 4.5 and 5.5 years of age. The internalizing scales are most directly related to the psychological stress hypothesis of TEDDY. Children with high internalizing scale scores are considered particularly stress-reactive (Calkins et al, 2007; Lengua et al, 2006; Smider et al, 2002).

The CBCL will be used together with the Stressful Life Event data to test whether children who develop persistent beta-cell autoimmunity experienced greater life stresses and higher internalizing scores on the CBCL than those who do not develop autoimmunity. We are particularly interested in the interaction between a child's internalizing scores and the number of stressful experiences in the child's life. We expect the high frequency of negative life events will have the greatest impact on beta-cell autoimmunity on children with high internalizing scores.

Because TEDDY collects data on illness episodes, we can also test the link between life stress, a child's internalizing scores, and the child's susceptibility to illness. The link between stress and illness has been well-established (Cohen, 2005; Miller and Cohen, 2005; Wright et al., 2005). It is possible that stress has an indirect effect on the development of T1DM through this mechanism; children who have high internalizing scores and who experience more stress may be more susceptible to illness. Illness in turn, may be linked to the development of autoimmunity and T1DM – one of the primary study hypotheses.

Because the CBCL is so well normed, it can provide important information about the impact of TEDDY on the child. Rates of externalizing and internalizing behavior comparable to normative samples would suggest that TEDDY children are not suffering unnecessarily from their identification of increased T1DM risk in the absence of any means to prevent the disease.

As with any normal sample of children, we expect some children to exhibit elevated internalizing and externalizing scores. Children with elevated scores may be at increased risk for study drop-out. Those with high internalizing scores may show heightened distress to the blood draws, leading parents to drop-out of the study. Those with high externalizing behaviors are often oppositional and exhibit significant behavior problems. Parenting such children is particularly challenging (Paley et al, 2006) and the demands of the

TEDDY protocol may be more than a parent of such a child can manage, leading to study drop-out.

As children age, it will be important to gather self-report data on their psychological functioning. Given the lengthy nature of the CBCL, TEDDY will move from the CBCL (parent-report only) to the Strengths and Difficulties Questionnaire (SDQ) (parent- and child-report) at 11.5 and 13.5 years of age (Goodman, 1997; Goodman et al., 1998). The SDQ is a wellvalidated screening instrument used in the US National Children's Study as well as internationally in TEDDY countries (Hintermair, 2006; Koskelainen et al., 2000; Malmberg, et al., 2003) that assesses child psychological functioning across five behavioral and emotional domains. The SDQ has 25items and will allow a determination of whether TEDDY children are comparable to children from the general population in terms of their psychological and behavioral functioning. The SDQ has been cross-validated with the CBCL, thus past TEDDY data using the CBCL can be easily compared (Goodman et al., 1999).

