## 4. Objectives

The primary objective of this study is to identify environmental factors that predispose to or protect from beta-cell autoimmunity and T1DM.

The secondary objectives include:

[figure not shown]
- 1. Identification of potential differences in the environmental determinants of T1DM across diverse populations and ethnic groups.
- 2. Identification of potential differences in the environmental determinants of T1DM between children with and without first-degree T1DM relatives.
- 3. Establishment of a central repository for data and biologic samples for subsequent hypothesis based research.
- 4. Exploration of psychosocial corollaries of the ascertainment of risk status for autoimmunity and T1DM in newborns.
- 5. Exploration of gene-environmental interactions.
- 6. Better understanding of the natural history of the disease.

[figure not shown]

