## 8.12.4.7. Identifying Family Characteristics that Discriminate Study Completers from Study Drop-Outs

To improve study efficiency and participant retention, it will be important to identify family characteristics predictive of study completion and drop out. Both demographic and psychosocial measures will be assessed for this purpose. These data will be collected by questionnaire or other study procedures, as described previously.

**Demographic predictors.** Likely candidates for demographic predictors of study retention and drop out include: family history of diabetes; convenience to the study site (including travel distance and time); expenses associated with study visits; availability of transportation to study visits; parental employment and whether work must be missed for study visits; extent of other child-care or family-care demands; child birth order; child gender; parental age, parental

education, parental income; single-parent status, child and parent race, and study site.

**Psychosocial predictors.** Likely candidates for psychosocial predictors of retention and drop-out include: parental anxiety and diabetes worry in response to the child's at-risk status (with high anxiety and diabetes worry associated with study retention); parental beliefs about the likelihood the child will develop diabetes (with parental beliefs that the child will never develop diabetes associated with drop-out); parental depression (with high depression more likely to be associated with drop out); negative life events in the parent or child (high number associated with drop-out); parental concerns with confidentiality or possible loss of medical insurance (higher concern associated with drop-out); parental satisfaction (low satisfaction associated with drop-out). Certainly the relative contribution of father vs. mother assessments on these variables is of interest, and may differ across cultures. Once the child reaches the age of assent, child variables may become predictive of study retention or drop-out.

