All analyses will be performed using SAS (version 9 or later). Among the procedures to be used will be Proc Logistic, Proc Lifetest, and Proc Phreg, and Proc Lifereg. Observations with missing values of a variable will be omitted from those analyses using that variable, but not from analyses not using those variables. No data imputation methods will be applied to missing values. Programs will be written to check all data for values that are out of range or inconsistent. Reports of such data will be sent to the P.I., discussed, and corrected and the data corrected as appropriate. Indications of confusing data forms or data entry problems will be remediated.

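### CBCL rates near the norm among children who stay are only limited evidence of no harm, because high scorers may leave and only available scores are analysed

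*Protocol*

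**What the plan says.** Section 8.12.4.6 has one parent complete the CBCL when the child is 3.5, 4.5 and 5.5 years old. Besides testing the stress hypothesis, the scores are to inform on the study's effect on the child: "Rates of externalizing and internalizing behavior comparable to normative samples would suggest that TEDDY children are not suffering unnecessarily" from being identified as at risk. Shortly afterwards the section says: "Children with elevated scores may be at increased risk for study drop-out". It gives two mechanisms, both tied to the study itself: distress at blood draws, and visit demands that are too much for the parent of an oppositional child. A similar comparison with the general population is planned with the Strengths and Difficulties Questionnaire (SDQ) at 11.5 and 13.5 years.

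The concrete missing-data rule is in section 10.1: "Observations with missing values of a variable will be omitted from those analyses using that variable", and "No data imputation methods will be applied to missing values". Section 10.8 adds a general commitment to accepted methods that avoid bias. It names none for questionnaire scores, and the registries it cites recover diabetes diagnoses only.

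Section 8.12.4.7 plans to look for predictors of completion and drop-out: "Both demographic and psychosocial measures will be assessed for this purpose". Its listed candidates include parental anxiety ("with high anxiety and diabetes worry associated with study retention"), depression, life events and satisfaction. On the child it says: "Once the child reaches the age of assent, child variables may become predictive of study retention or drop-out". Section 10.2.2 plans continuous comparison of drop-outs with continuing subjects on demographics and exposures. Sections 8.12.4.3 and 8.12.4.4 ask leavers about their experience and reasons, but not with the CBCL.

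**The concern.** If leaving depends on the score, the share of elevated scores among children still attending is not the share in the enrolled cohort. The protocol names that dependence as a possibility, fixes an available-case analysis, and reads similarity to norms as reassuring. The three statements are not connected. A rate near the norm could come from no excess of problems, or from an excess that has partly left the study.

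The comparison serves a stated secondary objective (section 4): "Exploration of psychosocial corollaries of the ascertainment of risk status for autoimmunity and T1DM in newborns". False reassurance would bear on the case for telling families about newborn genetic risk when nothing can prevent the disease.

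**Working it through.** The protocol states no figure for this comparison, so there is nothing to reproduce. The calculation below is an illustration.

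**Inputs**
- From the protocol: annual losses of 2, 5 and 10% (non-zero scenarios of section 10.3), 8,677 children followed (section 1, Design), assessment at 5.5 years.
- Assumed: normative rate of elevated scores 10%; true cohort rate p = 15% (then 12.5%); drop-out hazard ratio HR for elevated versus other children of 2, 1.5 or 0.75; differential loss starting at birth (d = 5.5 years) or at the first CBCL (d = 2 years); elevated status fixed over time.

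**Formula.** With annual loss L, h0 = −ln(1 − L)/(1 − p + p·HR), s0 = exp(−h0·d), s1 = exp(−HR·h0·d). Observed rate = p·s1/[p·s1 + (1 − p)·s0].

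**Worked case** (p = 0.15, HR 2, L = 5%, from birth): h0 = 0.05129/1.15 = 0.0446; s0 = 0.7825; s1 = 0.6122; observed = 0.0918/(0.0918 + 0.6651) = 12.1%.

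**Observed rate at 5.5 years, true rate 15%**

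| Start | HR | 2% | 5% | 10% |
|---|---|---|---|---|
| Birth | 2 | 13.8 | 12.1 | 9.6 |
| Birth | 1.5 | 14.4 | 13.4 | 11.9 |
| Birth | 0.75 | 15.4 | 16.0 | 17.0 |
| 3.5 y | 2 | 14.6 | 13.9 | 12.8 |
| 3.5 y | 1.5 | 14.8 | 14.4 | 13.8 |
| 3.5 y | 0.75 | 15.1 | 15.3 | 15.7 |

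**Against sampling error.** The number remaining is n = 8,677 × (1 − L)^(5.5 − d) × [p·s1 + (1 − p)·s0], and the half-width is 1.96·√[rate(1 − rate)/n]. In the worked case n = 6,568 and the half-width is 0.79 points. For HR 2, the downward bias at 2, 5 and 10% loss is 1.2, 2.9 and 5.4 points from birth (half-widths 0.77, 0.79, 0.82). From 3.5 years it is 0.4, 1.1 and 2.2 points (half-widths 0.78, 0.84, 0.94).

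**Would the excess be hidden?** In 11 of the 12 cells with HR 2 or 1.5, the lower 95% limit stays above 10%; the lowest of these is 11.88 − 0.91 = 10.97%. The exception is HR 2 from birth at 10% loss. Setting the observed rate to 10% and solving for HR gives about 12, 3.2 and 1.9 from birth. From 3.5 years there is no solution at 2% loss (the limit is 11.88%), and the values at 5 and 10% are about 15 and 4.3.

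**A smaller excess, true rate 12.5%.** The same formulas give 11.5, 10.0 and 7.9% (HR 2) and 11.9, 11.1 and 9.8% (HR 1.5) from birth; from 3.5 years, 12.1, 11.5 and 10.6% and 12.3, 12.0 and 11.5%. In four of these 12 cells the lower limit is below 10%: HR 2 from birth at 5 and 10% loss, HR 1.5 from birth at 10%, and HR 2 from 3.5 years at 10% (10.59 − 0.86 = 9.73%).

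**Check in another form.** Let r be retention of elevated scorers divided by retention of others; observed = p·r/(p·r + 1 − p). A true 15% looks like 10% when r = (0.10/0.90) × (0.85/0.15) = 0.63. Losses of 10% versus 2% a year give r = (0.90/0.98)^5.5 = 0.626 and an observed 9.95%. A true 12.5% needs r = 0.78; losses of 10% versus 5% give 0.784 at 4.5 years and an observed 10.07%.

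**The case against.** The sentence is hedged and is not a decision rule, and the CBCL is not the only assessment of harm: parental anxiety and depression, child reactions, satisfaction and leavers' questionnaires also address it. The illustration seldom produces the norm-like result that would trigger the reassuring reading. Loss that depends on behaviour from birth is hard to support for the externalizing mechanism, which does not describe infants. With a late start there is no bias at 3.5 years, and a child scored then who leaves later has already contributed that score. Weighting for retention is a method a protocol may leave to the analysis plan, and section 10.1 bars imputation, not weighting. Most of this stands, and it limits the weight of the point. It does not remove it: section 10.1 fixes an available-case rule, section 10.8 names no remedy for questionnaire scores, and the reading in 8.12.4.6 carries no caveat about loss.

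Three stronger readings are tempting but unsupported.
- A reader might infer that the protocol expects high scorers to leave. It says only that they may.
- A reader might infer that norm-like rates are no evidence at all. They are limited evidence, which the hedged wording partly conveys.
- A reader might infer that the CBCL is shut out of the drop-out analysis. Section 8.12.4.6 itself raises it as a possible predictor, and the list in 8.12.4.7 is of likely candidates under a general reference to psychosocial measures. The score is simply not named there.

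**Conclusion.** The point holds in a limited form. Norm-like CBCL rates among children who remain may partly reflect selective loss, and the analysis as written cannot tell this apart from a true absence of excess. Under the assumed 10% norm and HR of 1.5 or 2, the bias at 5.5 years is usually partial and rarely hides a true 15%; a true 12.5% is easier to hide. The direction is also open. If the parents of high scorers are anxious and anxious parents stay, as 8.12.4.7 suggests, the observed rate would overstate the problem (15.1 to 17.0% at HR 0.75). That still leaves the rate alone hard to interpret. The normative rate, true rate, hazard ratios and start of differential loss are all assumptions. Only an exploratory secondary objective is touched; the primary outcomes and power tables are not. This is a low-priority improvement.

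**What to change.** 1. Report CBCL and SDQ rates against norms twice: unweighted, and weighted by the inverse probability of remaining in the study with the instrument completed. Build the weights from the parental and demographic predictors of section 8.12.4.7, adding earlier CBCL scores for later visits.
2. Name the last available CBCL score among the drop-out predictors in 8.12.4.7. This makes explicit what 8.12.4.6 already suggests, and it estimates the differential loss that is only assumed above.
3. Qualify the sentence in 8.12.4.6, for example: *Rates close to the norms, before and after weighting for retention, would suggest no excess of problems among children who remain in the study.*

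The cost is extra analysis of data already collected, one reworded sentence and one named predictor; no visit or instrument is added. Weighted estimates are slightly less precise. They do not correct for unmeasured reasons for leaving, or for selective enrolment (8,677 followed of 21,589 eligible).
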